
and FFAs. The literature is not clear about this, with better availability from TAGs being reported in some studies in rats [15,16], better availability from PLs being reported in humans [17], and similar availability from TAGs and EEs being reported in other studies in rats [18] and in humans [19,20]. Reasons for the differences between studies probably relate to differences in how studies were done and how data are reported and interpreted. The n-3 fatty acids can be interesterified between different positions in the parent TAG molecule and this is done in some supplements to increase n-3 fatty acid bioavailability; specifically it is believed that the fatty acid at the 2-position of the TAG has better bioavailability. Whether EPA and DHA are equally available, or not, when presented in different forms is an important scientific question. We believe that the answer to this question is very important to regulators, advisors and consumers, as well as to those involved in the fish oil industry. Therefore, we propose to conduct research in human volunteers that will address this question. We plan to investigate the appearance of EPA and DHA in the bloodstream over a period of weeks of consumption of those fatty acids in different chemical forms.

8. Objectives

The overall objective will be to follow the appearance of EPA and DHA in blood components when the fatty acids are consumed either as TAGs (two different formulations, one with the n-3 fatty acids interesterified and one without this modification), EEs, or FFAs.

The specific objectives are:

- 1. To follow the appearance over several weeks in plasma lipids and blood cells of EPA and DHA consumed as components of either TAGs or EEs or FFAs.
- 2. To follow the effect of the different omega-3 formulations on blood markers of inflammation (e.g. cytokines, adhesion molecules).

9. The study

General approach to be taken

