Long term (several weeks to several months) studies are required to investigate and to compare the incorporation of n-3 fatty acids into transport pools (blood lipids) and functional pools (e.g. cells) which is a true measure of n-3 status. When included in the human diet EPA and DHA are incorporated into plasma lipid fractions, platelets, white cells, red cells and many other cell and tissue types. We have studied the detail of such fatty acid incorporation, particularly for plasma phospholipids and for white blood cells in at least eight studies in human volunteers and also in patients with advanced atherosclerosis and with Crohn's Disease. In these studies fish oil supplements of various types (but almost exclusively in the TAG form) have been used with blood being sampled at various time intervals over the course of several months. We have reported both the time- and dose-dependent nature of the incorporation into plasma phospholipids and white blood cells (e.g. see [21]). Incorporation of EPA and DHA is typically detectable within weeks. However the rate of incorporation and the time to reach a maximum varies according to turnover of the pool investigated. Thus incorporation into white cells is faster than into red cells. We will use the general approach used in our previous studies with human volunteers to investigate the appearance in plasma lipids (phospholipids, TAGs, cholesteryl esters, NEFAs, EEs), in white cells (mononuclear cells) and in red cells of EPA and DHA when supplemented in the TAG or EE or FFA form.

Subjects and supplements

Healthy males and females aged 18 to 45 years with a body mass index between 20 and 32 kg/m^2 (n = 100) will be recruited. Subjects will recruited via posters; email shots in the University of Southampton, Southampton General Hospital, and other organisations with which the researchers have contact; advertisements in local newspapers. Subjects who express an interest will be screened by telephone interview. If they fit the inclusion and exclusion criteria (see below) they will be sent the information sheet. They will be contacted about 7 days later to confirm their interest or not, and if they remain interested an appointment will be made for them to visit the Wellcome Trust Clinical Research Facility, Southampton General Hospital.

Recruited subjects will be randomised to one of five groups (n = 20 per group):

- Placebo
- Omega-3 ethyl esters
- Omega-3 free fatty acids

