- Omega-3 triglycerides (standard formulation)
- Omega-3 triglycerides (interesterified formulation).

The n-3 fatty acid preparations to be used are all commercially available as supplements and will be provided in capsules. Approximately 1.5 g EPA plus DHA (approx. 1.1 g EPA and 0.4 g DHA) will be given per day. Subjects, researchers and clinical staff will be blinded to group allocation.

Inclusion criteria

- 1. Aged 18 to 45 years
- 2. Body mass index 20 to 32 kg/m^2
- 3. Not consuming fish oil or other oil supplements
- 4. Not eating more than one oily fish meal per week
- 5. Willing to adhere to the study protocol
- 6. Being able to provide written informed consent

Exclusion criteria

- 1. Aged < 18 or > 45 years
- 2. Body mass index $< 20 \text{ or} > 32 \text{ kg/m}^2$
- 3. Being diabetic (type 1 or type 2)
- 4. Use of prescribed medicine to control inflammation
- 5. Chronic gastrointestinal problems (e.g. IBD, IBS, celiac disease, cancer)
- 6. Allergic to fish
- 7. Participation in another clinical trial
- 8. Use of fish oil or other oil supplements

Subject participation schedule

Subjects who express an interest will be screened by telephone interview. If they fit the inclusion and exclusion criteria they will be sent the information sheet. They will be contacted about 7 days later to confirm their interest or not and if they remain interested an appointment will be made for them to visit the Wellcome Trust Clinical Research Facility, Southampton General Hospital. At the first (and all subsequent) visit, subjects will attend in the fasted state (no food or drink except water after 9 pm the previous evening).

Subjects will visit the Wellcome Trust Clinical Research Facility, Southampton General Hospital on six occasions each between 8 and 10 am. On each occasion they will be in the fasted state. Visits will be at study entry and after approx. one, two, four, eight and twelve weeks of supplementation. On each occasion blood (20 ml) will be taken into heparin; at the visit made at study entry height and weight will be measured. At the end of each visit subjects will be offered toast and a hot drink. Subjects will receive a supply of supplements along with instructions on how to take them at the first study visit.

Sample analysis

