Blood will be used to prepare plasma, mononuclear cells and red cells. Plasma will be aliquoted and frozen at minus 80°C. Mononuclear cells will be frozen at minus 80°C. Red cell membranes will be prepared using standard techniques currently in use in the PI's lab and then frozen at minus 80°C. Lipid will be extracted from plasma, mononuclear cells and red cells using chloroform/methanol. Plasma TAGs, PLs, NEFAs and EEs will be isolated by solid phase extraction [21]. The fatty acid composition of plasma TAGs, PLs, NEFAs and EEs and of mononuclear cells and red blood cells

will be determined by gas chromatography. Inflammatory marker concentrations in blood will be measured by flow cytometry.

10. Data handling and record keeping

- All data will be entered onto a spreadsheet (Microsoft Excel) by the researchers involved.
- All data will be entered on a password-protected computer. This data will be accessed only by the PI and the researchers involved.
- All data will only be linked to study codes and thus not identifiable with the source volunteer. However, the caveat to this will be a data set recording the volunteer name and study code without any other volunteer details.
- All data recorded on paper will be kept in a locked filing cabinet in the researchers' office and/or in a dedicated, restricted access, clinical data storage area on Level D of the IDS Building, University of Southampton.
- Data of an identifiable nature (i.e. volunteer names, contact details, addresses) will be destroyed 12 months after the end of the study. All other data will be kept securely for 15 years and then destroyed.
- Data will be obtained, handled and stored in adherence to the principle set out in the Data Protection Act 1998.
- The investigators and the Institute of Human Nutrition will permit monitoring, audits, REC and MHRA review (as applicable) and provide direct access to source data and documents.

11. Statistical Analysis

The statistical analysis will involve:

- comparison of the change in EPA content of plasma phospholipids from study entry to week 12 between the different treatment groups (the primary outcome). This will be performed by one factor ANOVA.
- comparison of the change in EPA content of each of the other plasma lipid pools and of mononuclear cells and red blood cells from study entry to week 12 between the different treatment groups (the primary outcome). This will be performed by one factor ANOVA.

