- comparison of the change in DHA content of each of the plasma lipid pools and of mononuclear cells and red blood cells from study entry to week 12 between the different treatment groups (the primary outcome). This will be performed by one factor ANOVA.
- comparison of the change of the EPA and DHA contents of each plasma lipid pool and of mononuclear cells and red blood cells over time following consumption of n-3 fatty acids in each chemical form. This analysis will be performed using two-factor repeated measures ANOVA, the two factors being time and group (i.e. "treatment").
- comparison of the change over time in blood concentrations of inflammatory markers according to treatment group. This analysis will be performed using two-factor repeated measures ANOVA, the two factors being time and group (i.e. "treatment").

All statistical comparisons will be performed at the end of the study using SPSS.

12. Sample size calculation

The study is powered according to the anticipated change in EPA content of plasma phospholipids (this is similar to the anticipated change in EPA in mononuclear cells and in red cells). Based upon previous studies of this sort, a supplement providing 1.1 g EPA/day is expected to increase the EPA content of plasma phospholipids by 100% from approximately 1 to approximately 2% of total fatty acids. It is considered that a 25% lower incremental increase in EPA content is meaningful. Typical standard deviations for the incremental increase in EPA content of plasma phospholipids from our previous studies are approximately 0.25%. Thus, sample size was calculated using mean values of 1 and 0.75 for the two groups, respectively, and standard deviations of 0.25 for each group. A sample size calculator revealed that a sample size of 17 per treatment group will give 90% power of

detecting this effect (i.e. a 25% increase) as statistically significant, by a pairwise comparison and setting P < 0.05, as is usual. In order to allow for a drop-out rate of 20% 20 subjects per group will be recruited (100 subjects in total).

13. Safety assessments

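### Inflammatory markers are tested only by a group-by-time repeated measures ANOVA, with no contrast against placebo, so a small to moderate effect shared by the n-3 forms would probably be missed

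*Protocol*

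**What the plan says.** Protocol section 8 gives the second specific objective as "To follow the effect of the different omega-3 formulations on blood markers of inflammation (e.g. cytokines, adhesion molecules". Section 9 randomises to five groups of 20: placebo and four n-3 preparations. One daily amount is stated for the preparations: "Approximately 1.5 g EPA plus DHA (approx. 1.1 g EPA and 0.4 g DHA) will be given per day". On sampling: "Visits will be at study entry and after approx. one, two, four, eight and twelve weeks of supplementation". Blood is drawn at each of these six visits. On the assays the Protocol says only "Inflammatory marker concentrations in blood will be measured by flow cytometry", without naming the visits at which this is done.

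Section 11 gives the markers a single bullet, "comparison of the change over time in blood concentrations of inflammatory markers according to treatment group", to be analysed by repeated measures ANOVA with time and group as the two factors. EPA and DHA get the same type of analysis and, in addition, a one-factor ANOVA of the change from entry to week 12. Section 12 bases the sample size on plasma phospholipid EPA alone. No effect size, standard deviation or power is given for any inflammatory marker.

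**The concern.** The ANOVA poses its question through one omnibus interaction. If the n-3 forms act on a marker in much the same way, the signal is a single difference, n-3 against placebo, emerging over some weeks. The omnibus test spreads that signal over every group-by-visit pattern and loses power. The other group term in the same ANOVA is no substitute: the group main effect averages in baseline and the early visits.

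A significant interaction would not say whether a marker rose or fell, in which arm, or relative to what. A non-significant one could be reported as absence of an effect on inflammation when the test had little chance of finding it. One fifth of the subjects receive placebo, yet no named marker test compares against them directly.

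**Working it through.** **Plan's own figure.** The only power statement is for EPA: 17 per group for 90% power, difference 0.25, SD 0.25. The formula 2(z_α + z_β)²(SD/difference)² gives 2(1.645 + 1.282)² = 17.1 for a one-sided 5% test, so the stated figure is reproduced on that basis. It says nothing about the markers, so no planned marker power can be checked.

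**Inputs.** From the Protocol: 5 groups, 20 recruited per group, 20% drop-out (20 × 0.8 = 16 completers), visits at weeks 0, 1, 2, 4, 8 and 12, α = 0.05. Assumed here: two-sided testing, marker assays at all six visits, a common effect in the four n-3 arms, its size and its time course.

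**Step 1: degrees of freedom.** Group-by-time: (5 − 1) × (6 − 1) = 20. If markers were assayed only at entry and week 12: (5 − 1) × (2 − 1) = 4.

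**Step 2: cost of the degrees of freedom.** A noncentrality of 8.01 gives 80% power on 1 df and 30% on 20 df.

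**Step 3: closed form.** Let d be the shared effect at week 12 in SDs of the week-12 change, n the number per arm, and f the fraction of the effect present at each visit. Under compound symmetry:

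- 1-df pooled contrast of the week-12 change: λ = d² × 4n/5.
- 20-df interaction: λ = (8/5) × n × d² × S, where S is the sum of squares of f about its mean.

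Example with n = 16, d = 0.5 and f = 0, 0.25, 0.5, 1, 1, 1. The mean of f is 0.625 and S = 3.3125 − 6 × 0.625² = 0.969. The interaction has λ = 1.6 × 16 × 0.25 × 0.969 = 6.2, power 23%. The contrast has λ = 0.25 × 12.8 = 3.2, power 42%.

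The interaction ranges below cover four time courses: step from week 1, linear ramp, full by week 4, and full at weeks 8 and 12 only.

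| n per arm | d | 20-df interaction | 1-df week-12 contrast |
|---|---|---|---|
| 16 | 0.5 | 18-32% | 42% |
| 16 | 0.8 | 48-80% | 81% |
| 20 | 0.5 | 22-42% | 51% |
| 20 | 0.8 | 60-90% | 89% |
| 20 | 1.0 | 85-99% | 98% |

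With assays at entry and week 12 only, the 4-df test has 25% at n = 16, d = 0.5. The shortfall therefore does not depend on six assays.

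**Step 4: baseline-adjusted contrast.** Now let d be in SDs of the marker at one visit and r the correlation between entry and week 12. ANCOVA gives λ = d²/(1 − r²) × 4n/5. With n = 16 and d = 0.5:

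- r = 0.6: 0.25/0.64 × 12.8 = 5.0, power 60%.
- r = 0.9¹² = 0.28: 0.25/0.92 × 12.8 = 3.5, power 45%.

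**Step 5: simulation.** 16 per arm, covariances from compound symmetry 0.6 to 0.9^weeks, Greenhouse-Geisser correction for the interaction, d on the scale of step 4.

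- Shared effect of 0.5 SD, full from week 4 or emerging at weeks 8-12 (half, then full): interaction 19-29%, pooled week-12 ANCOVA contrast 46-61%. At least one of four Bonferroni-adjusted form-versus-placebo contrasts (each at 0.05/4 = 0.0125) is significant in 35-49%.
- Other time courses at 0.5 SD: interaction 15-23% (step), 16-21% (linear), 26-39% (full at both weeks 8 and 12). The week-12 contrast stays at 45-60%.
- Group main effect of the ANOVA at 0.5 SD, full by week 4: 16-17%.
- Only one form acts, 0.8 SD: interaction 50-73%, pooled contrast 11-15%, four adjusted form contrasts 44-61%.

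**The case against.** The strongest reply is that a shared effect is nowhere a hypothesis of this trial. Objective 2 speaks of the different formulations, and the background treats equal availability of the forms as an open question. An omnibus group-by-time test fits that wording, and the last line of the working shows that it is far better than a pooled contrast if one form alone acts. This stands. A reader might infer that the pooled contrast should replace the ANOVA, or that most of the 20 df go on patterns of no interest. The documents support neither, because differences between forms are part of the question.

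The size of the marker effect is also unknown. At 0.5 SD even the focused contrast has only about 45-60% power, so part of the risk is sample size, in a study powered on EPA alone. This stands too.

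Averaging weeks 4, 8 and 12 looks better still (68-82% at 0.5 SD when the effect is full from week 4), but that depends on the assumed time course. If the effect emerges at weeks 8-12, the average gives 23-28% against 20-26% for the interaction. Week 12 is the safer target.

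Finally, sphericity correction, transformation and follow-up comparisons are commonly left to a SAP, which is not shown. Their absence is not held against the Protocol. What remains is that section 11 does choose tests outcome by outcome, gives EPA and DHA a week-12 comparison, and fixes only the omnibus test for the markers.

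**Conclusion.** The point holds in a limited form. The one test named for objective 2 is weak against a small to moderate effect common to the n-3 forms. At about 0.5 SD with 16 completers per arm it has roughly 20-30% power, against 45-60% for a baseline-adjusted week-12 contrast. Across less and more favourable time courses the interaction ranges from 15% to 39%. Whatever its result, it does not show direction or arm.

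This rests on three assumptions that the Protocol does not state: a shared effect, which one stated daily dose makes plausible; its size; and, for the 20 df, assays at all six visits.

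A reader might infer that any real effect on inflammation is likely to be missed. That goes too far: with 20 per arm the interaction has 60-90% power at 0.8 SD of change and 85-99% at 1.0 SD. Nor do the documents support saying that the placebo arm exists mainly for objective 2, since section 11 compares all treatment groups on EPA and DHA as well. This is a worthwhile improvement to a secondary analysis and leaves the primary outcome untouched.

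**What to change.** In the section 11 bullet on inflammatory markers, keep the repeated measures ANOVA for the time course and for differences between forms. Add, for each marker, an ANCOVA of the week-12 value with the entry value as covariate, reporting with confidence intervals:

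- the contrast of the four n-3 arms pooled against placebo (1 df);
- the four form-versus-placebo contrasts, Dunnett- or Bonferroni-adjusted, and not conditional on the pooled contrast or the omnibus test.

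State at which visits the markers are assayed.

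The cost is wording only, with no extra subjects or samples, plus five more contrasts per marker on a secondary objective. The pooled contrast is weak if a single form acts. The form-versus-placebo contrasts and the retained interaction cover that case: at 0.8 SD the former fall only modestly below the interaction (44-61% against 50-73%).

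### Section 12 claims 90% power at 17 per group, but its inputs give about 81% under a two-sided 5% test; 90% needs 22 to 23 per group

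*Protocol*

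**What the plan says.** Section 12 bases the sample size on the change in EPA content of plasma phospholipids, the primary outcome. It expects 1.1 g EPA per day to raise this content from about 1% to about 2% of total fatty acids, and it treats an increment smaller by a quarter as meaningful. It then says that "sample size was calculated using mean values of 1 and 0.75 for the two groups, respectively, and standard deviations of 0.25 for each group". The result is given as "A sample size calculator revealed that a sample size of 17 per treatment group will give 90% power of" detecting that effect, "by a pairwise comparison and setting P < 0.05, as is usual".

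The section does not say whether the test is one-sided or two-sided. Section 11 gives the primary analysis as a comparison of the week-12 change between treatment groups: "This will be performed by one factor ANOVA". Section 9 sets five equal groups of 20.

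**The concern.** A standardised difference of 1 is a familiar case. For 90% power at a two-sided 5% level it needs a little over 20 per group, so 17 looked too small. Seventeen is, however, what a two-sided t-test needs for 80% power.

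This is the protocol's only power statement, and it supports the primary outcome. The trial asks whether the chemical forms of EPA and DHA are equally available, so a non-significant difference between forms may well be read as evidence that they are. How far that reading is safe depends on the power, and an overstated figure would lend it too much weight.

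**Working it through.** **Inputs, all from section 12:** difference δ = 1 − 0.75 = 0.25; SD σ = 0.25 in each group; pairwise comparison; α = 0.05; 17 per group; stated power 90%. Sidedness is not given, so both readings were tried.

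**Standardised difference:** d = δ/σ = 0.25/0.25 = 1.

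**1. Trying to reproduce the 90%.**

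Normal approximation, n per group = 2(z₁₋α + z₁₋β)²/d²:
- One-sided 5%: 2 × (1.645 + 1.282)² = 17.1, which rounds up to 18.
- Two-sided 5%: 2 × (1.960 + 1.282)² = 21.0 (21.01 unrounded), which rounds up to 22.

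Power at n = 17, with d√(n/2) = √8.5 = 2.916:
- One-sided: Φ(2.916 − 1.645) = 0.898. The noncentral t gives 0.8865.
- Two-sided: Φ(2.916 − 1.960) = 0.830.

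So the stated figure is reproduced, to within about 1.5 percentage points, only by a one-sided test. Even then 17 falls just short: the unrounded n for 90% is 17.13 (normal) or 17.85 (t).

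**2. Two-sided power by sample size.** The t-test column uses the noncentral t with 2n − 2 degrees of freedom and noncentrality √(n/2). The pooled column keeps the same noncentrality but takes the error term from all five groups, with 5(n − 1) degrees of freedom.

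| n per group | t-test | normal approx. | pooled ANOVA error |
|---|---|---|---|
| 16 | 0.7814 | 0.8074 | 0.7973 |
| 17 | 0.8070 | 0.8303 | 0.8213 |
| 20 | 0.8690 | 0.8854 | 0.8790 |
| 22 | 0.8997 | 0.9126 | 0.9076 |
| 23 | 0.9125 | 0.9238 | 0.9195 |

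No two-sided pairwise method reaches 90% at 17, or even at the full 20 recruited.

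**3. Sample size by two-sided t-test.** For 90% power the unrounded n is 22.02, so 23 (22 gives 89.97%). For 80% power it is 16.71, which rounds up to 17, the number in the protocol.

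**4. What 17 per group can do at 90% power.** The two-sided t-test needs d = 1.147. The detectable difference is 1.147 × 0.25 = 0.287, about 29% of the expected increment of 1, rather than 25%. Equivalently, keeping the difference at 0.25, the SD would have to be 0.25/1.147 = 0.218.

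**5. Type II error.** 1 − 0.807 = 0.193, against the 0.10 implied.

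**The case against.** The strongest reply is that sidedness is not among the stated inputs. A one-sided 5% test gives 89.8% by normal approximation, so the figure may be an undeclared one-sided calculation and not an arithmetic slip. The text has some directional colour: section 12 describes the effect of interest as a lower increment, and the background reports a belief that the 2-position of the triglyceride favours bioavailability.

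That stands as a possible account of where 17 came from. It does not rescue the statement. No one-sided test is declared anywhere, and the appeal to the usual P < 0.05 points to the conventional two-sided threshold. The ANOVA F test has no direction. The background calls the literature unclear and leaves open whether the forms differ at all. Section 12 itself calls the same effect first a lower increment and then an increase.

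Other points stand in part:
- The pooled error term lifts the power to 82.1%, so 81% to 83% is the fair range.
- The planning values are approximate, and an SD of 0.218 would restore 90%. But the protocol states 0.25, and the power must follow from that.
- The protocol does not say how a null result will be read, so the consequence for interpretation is a risk and not a certainty.
- Section 12 allows for 20% drop-out from 20 per group, which leaves 20 × 0.8 = 16, not 17. This is a separate matter. It makes the position slightly worse: 78.1% by two-sided t-test.

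**Conclusion.** The power statement is wrong as written for the analysis planned. With the protocol's own means and SD, 17 per group gives about 81% power by a two-sided t-test, and at most 83% by the other two-sided pairwise methods tried. Ninety per cent needs 22 per group (normal approximation or pooled error) or 23 (t-test). The chance of missing the target difference is about 19%, roughly twice that implied.

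This rests on one assumption that the protocol does not spell out, a two-sided 5% test, which is the natural reading of sections 11 and 12. It also takes each pairwise comparison at an unadjusted 5%, as section 12 does. On the one-sided reading the figure is nearly right, but the power calculation would then not match the analysis.

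**What to change.** Replace the power sentence in section 12 with, for example: *With 17 evaluable subjects per group, a two-sided t-test at the 5% level has 81% power to detect a difference of 0.25 between two groups, assuming an SD of 0.25; the difference detectable with 90% power is 0.29.* It would help to add that at 16 completers per group, which is what 20% drop-out from 20 leaves, the power is 78%.

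The cost is one or two sentences and a less favourable stated power. No extra subjects are needed, and the design and analysis do not change.

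If the sponsor wishes to keep 90% instead, 22 to 23 evaluable subjects per group are required. With 20% drop-out that means recruiting 22/0.8 = 27.5, so 28, or 23/0.8 = 28.75, so 29 per group: 140 or 145 subjects over five groups in place of 100.

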The supplements to be used are commercially available and are safe. The sole invasive procedure to be used is obtaining blood samples; this will be done by trained nursing staff limiting the likelihood of adverse events related to participation in the study. However if any volunteer reports any untoward medical occurrence this will be recorded on an adverse event or serious adverse event form and the PI informed immediately. If the investigator suspects that a serious adverse event is either a) related to the intervention or b) unexpected, the PI will report the event to the main REC and to a representative of the supplier of the supplements. An adverse or serious adverse event may result in the volunteer wishing to withdraw from the study or being unable to continue with the study schedule. In this case or any other instance in which a subject withdraws or is withdrawn from the study a volunteer withdrawal form will be recorded on the form. The subject will not be required to give any reason for withdrawing themselves from the study and will not be asked to do so by the investigator.

14. Stopping/Discontinuation of intervention

Completion of each subject's involvement in the study will be when the last blood sample is taken, which will be approx. 12 weeks after the subject entered the study. If there is any reason for discontinuing the intervention prior to its completion the PI will arrange for the research team to inform all volunteers immediately. The PI will also inform the sponsor and the main REC.

15. Monitoring

The project will be overseen and monitored by the Southampton University Hospitals Trust R&D Office.

Steps taken to ensure quality of research

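### Adverse event recording depends on a volunteer's report, and no standard health enquiry is listed at the five on-supplement visits, so events are likely to be under-recorded in all arms

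*Protocol*

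**What the plan says.** Protocol section 13 (Safety assessments) states the trigger for recording an event: "if any volunteer reports any untoward medical occurrence this will be recorded on an adverse event or serious adverse event form". Informing the principal investigator, and onward reporting of certain serious events, come after that step. On withdrawal the same section says: "The subject will not be required to give any reason for withdrawing themselves from the study and will not be asked to do so".

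Section 9 (Subject participation schedule) has subjects attend "on six occasions each between 8 and 10 am". The timing is: "Visits will be at study entry and after approx. one, two, four, eight and twelve weeks of supplementation". The procedures are: "On each occasion blood (20 ml) will be taken into heparin; at the visit made at study entry height and weight will be measured". Apart from fasting beforehand, light refreshment afterwards and the supply of supplements at the first visit, nothing else is listed. No health question appears.

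On masking, section 9 (Subjects and supplements) says: "Subjects, researchers and clinical staff will be blinded to group allocation". Section 16 adds that subjects can raise matters with the research staff, which again leaves the first move to the subject.

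**The concern.** The trial gives daily capsules for about 12 weeks, in four chemical forms or placebo, and sees every subject repeatedly during that time. When recording starts from a volunteer's report and no question is scheduled, what is captured depends on what each subject thinks worth mentioning. Mild or intermittent complaints are the ones most easily left out. The rule that withdrawing subjects are not asked why removes another occasion on which an event might come to light.

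At stake is the completeness of the safety record. Investigator review and any onward reporting can only act on events that have become known. A short list of events could also be taken as support for section 13's opening premise about the safety of the supplements, when it partly reflects how events were collected. How events are elicited is a data-collection matter for the protocol; no later analysis can recover events that were never recorded.

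**Working it through.** **Inputs**
- Trigger for recording: a volunteer's report (section 13).
- Visits: six in total, at entry and at about weeks 1, 2, 4, 8 and 12 (section 9).
- Groups: five, with 20 subjects each (section 9).
- Drop-out allowance: 20% (section 12).
- Not given in the protocol: adverse event rates and the share of events captured by report.

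**Step 1. Reproduce the visit count.** 1 entry visit + 5 on-supplement visits = 6, as stated. With no drop-out there are 5 × 100 = 500 on-supplement contacts. This is a maximum. If 20% drop out, 100 × 0.8 = 80 subjects complete, giving at least 5 × 80 = 400 contacts, so the range is 400 to 500.

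**Step 2. Set the text on capture against the text on visits.** Section 13 waits for a report. Section 9 lists the visit procedures and includes no enquiry that would prompt one. Section 16 leaves the initiative with the subject, and section 13 does not seek reasons for withdrawal. Together, the passages shown contain no point at which every subject is asked the same question.

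**Step 3. Does the shortfall differ between arms?** Let pA and pB be true event rates in two arms and s the share captured. The wording on collection is the same for every group, and subjects and staff are blinded, so s is expected to be the same in each.
- Recorded rates: s·pA and s·pB.
- Recorded ratio: s·pA / (s·pB) = pA/pB, unchanged.
- Recorded difference: s·(pA − pB), reduced in proportion to s.

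Under-recording therefore lowers all rates and weakens any contrast, but does not by itself create a difference. A spurious difference would need s to vary by arm, and nothing in the protocol points to that.

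**Step 4. What could the trial detect with full capture?** This uses assumed rates, for illustration only, with n = 20 per arm and a two-sided 0.05 level:

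power = Φ{[|pA − pB| − 1.96·√(2p̄(1 − p̄)/n)] / √([pA(1 − pA) + pB(1 − pB)]/n)}, where p̄ is the mean of pA and pB.

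- 40% v 20% (8 v 4 subjects expected): (0.200 − 1.96 × 0.1449)/0.1414 = −0.594, power 28%.
- 30% v 10% (6 v 2): (0.200 − 1.96 × 0.1265)/0.1225 = −0.39, power 35%.
- 50% v 20% (10 v 4): (0.300 − 1.96 × 0.1508)/0.1432 = 0.03, power 51%.

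Even perfect capture would leave comparisons between two forms weak. The benefit of asking is a more complete record, not a reliable test between forms.

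**Step 5. Effect on the stated analyses.** The primary outcome in section 11 is the change in plasma phospholipid EPA from entry to week 12, compared by one-factor ANOVA. No adverse event data enter it. The sample size in section 12 does not use them either.

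**The case against.** The strongest reply is that section 13 does not confine recording to unprompted reports: an answer to a question is also a report. Section 15 promises written procedures for every part of the study and good clinical practice throughout, and section 18 commits to ICH GCP. Those procedures and the case forms are not shown and may contain an enquiry. Tolerability is also neither an objective in section 8 nor an analysis in section 11, and Step 4 shows how little 20 per arm could reveal.

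This reply limits the point but does not remove it. A general promise of procedures and good practice does not replace the specific method that the safety section states, and neither that section nor the visit schedule sets a standard question. It does mean that under-recording is a likely risk and not an established fact.

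A reader might infer four stronger things that the protocol does not support:
- **That capture is uneven between the chemical forms.** Collection is identical and blinded in all arms, and how forthcoming subjects are is balanced in expectation by randomisation.
- **That nobody will be asked.** The protocol is silent on asking; it does not forbid it.
- **That events still open at week 12 get no follow-up.** Section 14 says "Completion of each subject's involvement in the study will be when the last blood sample is taken". That defines the end of participation and says nothing either way about following an open event.
- **That section 13 regards blood sampling as the only risk.** It calls it the only invasive procedure, and it separately provides for serious events suspected to be related to the intervention.

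**Conclusion.** The point holds in limited form. As written, the protocol makes adverse event recording depend on a volunteer's report and lists no standard enquiry at any of the five on-supplement visits. Events are therefore likely to be under-recorded, to a similar degree in all five arms.

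This rests on two assumptions: that visits run as section 9 lists them, without an enquiry added by procedures that are not shown; and that blinding holds, so that capture is alike across groups.

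The size of the shortfall cannot be given, because the protocol contains no event rates and no capture share. It is tempting to quote upper bounds for the case of no events in a group of 20, but such bounds reflect the group size and do not measure this defect. The primary outcome analysis and every stated figure stand. This is a worthwhile, low-cost improvement to safety capture, not a threat to the trial's main conclusion.

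**What to change.** Amend section 13 and the visit schedule in section 9. At weeks 1, 2, 4, 8 and 12, blinded staff ask every subject the same open, non-leading question about any health problems since the last visit. They record the answer, yes or no with details, on the existing adverse event form. Reports that subjects volunteer at other times continue to be recorded as now.

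The visits, staff and form are already in place. If the question takes about one minute (an assumption), the cost is 5 × 1 = 5 minutes per completing subject, or 400 to 500 minutes over the whole trial on the Step 1 range. The small downside is more minor events to record. The question reaches subjects only at visits they attend, so an event in someone who withdraws after their last visit could still be missed.
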